7.3. Study Drug Modifications

Study drug modifications will be summarized at the final analysis.

There are three types of study drug modification: dose reduction, cycle delay, and infusion interruption. The number of protocol-permitted dose reductions for each study drug are summarized in Table 5.

Table 5Protocol Permitted Dose Reduction by Study Drug

Study Drug	Number of Dose Reductions Allowed			
Trilaciclib/placebo	0			
Sacituzumab govitecan-hziy	2			

Study drug modifications will be summarized in each of the following categories: chemotherapy dose reduction, treatment cycle delay, and infusion interruption. The number and percentage of patients who had any chemotherapy dose reduction, any cycle delay, cycle delay due to hematological toxicity, or any infusion interruption will be summarized.

In addition, more detailed summaries outlined below will be provided.

Dose reduction for Sacituzumab govitecan-hziv. For Sacituzumab govitecan-hziy, the number and percentage of patients who had at least one dose reduction will be summarized. In addition, the number and percentage of patients will be summarized in the following mutually exclusive categories: "Not Applicable (cycle 1 treatment only)", 0, 1, or 2 reductions for the drug. The primary reason for dose reduction will be summarized.

Cycle delay. Information regarding whether a cycle was delayed was collected in the eCRF for each cycle. The number of cycles that have been delayed will be summarized as a continuous variable. In addition, the number and percentage of patients in each of the following mutually exclusive categories will be summarized: "Not Applicable (cycle 1 treatment only)", 0, 1, 2, …, maximum number of delays.

The reasons for cycle delay collected in eCRF are as follows:

- Low neutrophil count
- Low platelet count
- Both low neutrophil count and low platelet count
- Other hematologic toxicity
- Non-hematologic toxicity
- Other

Patients with reasons entered in the "Other" category will be further classified based on medical review of comments collected on the eCRFs into finer categories as appropriate.

Infusion interruption. Infusion interruption was captured in the eCRF for each study drug with the reasons. Any infusion interruption is defined as infusion interruption of any study drug.

The number of any and trilaciclib infusion interruptions will be summarized descriptively and categorically.

Corresponding data listings will be provided for dose modifications.

7.4. Duration of Total Follow-up

Duration of total follow-up will be summarized for the final analysis.

Duration of total follow-up (months) refers to the time interval that a patient participated in this clinical study starting from date of C1D1. It will be calculated based on the definition provided below.

Duration of total follow-up (months) = (date of death or date of last contact date known as alive - date of C1D1 + 1) / 30.4375.

The summary statistics for this variable will be included in the summary table for the OS analysis, and the patient level data will be included in the data listing described in Section 8.2.2.

G1 Therapeutics

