1.1. Study Design

This is a Phase 2, multicenter, open-label, single arm study evaluating the safety and efficacy of trilaciclib administered prior to sacituzumab govitecan-hziy in patients with unresectable, locally advanced or metastatic triple-negative breast cancer (TNBC) who received at least 2 prior treatments, at least 1 in the metastatic setting.

Approximately 45 patients were planned to be enrolled per Protocol Version 2.0. The sponsor decided to close enrollment to this study on February 14, 2023 in order to reallocate resources to other ongoing trilaciclib clinical trials. The final total number of patients enrolled in this study is 30.

Trilaciclib and sacituzumab govitecan-hziy will be administered intravenously (IV) in 21-day cycles as indicated below:

Trilaciclib:

Trilaciclib 240 mg/m2 administered as a 30-minute IV infusion completed within 4 hours prior to the start of sacituzumab govitecan-hziy on Day 1 and Day 8 of each 21-day treatment cycle.

Sacituzumab govitecan-hziy:

Sacituzumab govitecan-hziy 10 mg/kg administered IV on Day 1 and Day 8 of each 21-day treatment cycle. The first infusion is administered over 3 hours and patients are observed during the infusion and for at least 30 minutes following the initial dose for signs or symptoms of infusion-related reactions. Subsequent infusions may be administered over 1 to 2 hours if prior

infusions were tolerated, and patients should be observed during the infusion and for at least 30 minutes after infusion.

The study will include 3 study phases: Screening Phase, Treatment Phase, and Survival Followup Phase (Figure 1). The Treatment Phase begins on the day of enrollment and completes at the End of Treatment Visit. Survival Follow-up assessments should occur every 3 months after the End of Treatment Visit.

Figure 1 G1T28-213 Study Design Diagram

DC=discontinued; PD=progressive disease; PI=Principal Investigator; WD=withdraw

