2. THE NUMBER OF PLANNED ANALYSES

2.1. Final Planned Analysis - Analyses for Progression Free Survival, Tumor Response Endpoints, Myelosuppression Endpoints, and Overall Survival

The final planned analysis will be conducted when approximately 70% of patients have died (i.e., 21 deaths). Study database will be locked to support the final OS analysis. The following specified analyses will be performed:

- Analysis of progression free survival.
- Analysis of tumor response endpoints (ORR, CBR, and DOR).
- Analysis of myelosuppression endpoints.
- Analysis of overall survival.
- Analysis of safety data.

The final planned analysis will be used to support the abbreviated clinical study report (aCSR).

G1 Therapeutics

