4.2. Data Summary and Precision

General Principles of Data Summary

Data will be summarized for the respective analysis populations described in Section 3 in table format. All summary tables will only include an overall column for patients. In general, continuous variables will be summarized descriptively, i.e., the following summary statistics will be presented:

- Number of patients with non-missing data (indicated by n)
- Mean and standard deviation
- Median
- Q1 (first quartile) and Q3 (third quartile)
- Minimum and maximum values.

Categorical variables will be summarized categorically, i.e., number (n) and percentage of patients in each category will be presented.

General Principle of Data Listings

All collected data and derived variables will be included in patient data listings. An indicator will be provided for any imputed data element (e.g., imputed adverse event [AE] onset date). Columns in listings will be ordered by study site, patient ID, visit, and assessment or event date, if applicable, and then data elements.

General Principles of Precision for Summary Statistics and Calculated Statistical Quantities

The precision of summary statistics for continuous variables, including mean, median, Q1, Q3 minimum, and maximum, will be consistent with the precision of the variable as collected unless the collected data are integers. When the collected data are integers (whole numbers), the summary statistics of mean, median, Q1 and Q3 will be presented in the format with an additional digit after the decimal point. Calculated quantities of variability (e.g., standard deviation, standard error [SE]) will be presented with one more decimal place than the precision of the variable that is collected. The boundaries of a confidence interval (CI) will keep the same precision as the point estimate. The estimated adjusted relative risk will be reported with two decimal places.

For percentages, the total digits will be 3. That is, when the percentage has 2 digits prior to the

decimal point, there will only be 1 decimal place (e.g., 30.5%); while for a percentage that has only 1 digit prior to the decimal point, 2 digits places will be presented after the decimal point (e.g., 0.16%).

Rounding will take place after all calculation steps are completed prior to result display.

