8.1.3. Secondary Efficacy Endpoint – Analysis for Overall Survival

Overall survival is defined as the time (months) from the date of C1D1 to the date of death for patients who died in the study due to any cause or the time to the last contact date known to be alive for those patients who survived as of the final database lock for the final analysis (censored cases). OS will not be censored even if a patient receives subsequent anticancer treatments.

The analysis for OS will be based on the FAS.

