8.2.2. Analysis for Progression Free Survival (PFS) and Overall Survival

For PFS, the number and percentage of patients with a PFS event (radiographic disease progression or died due to any cause) or censored will be summarized along with the reasons for censoring. Furthermore, the number and percentage of patients with disease progression or who died due to any cause will be summarized with the number of PFS events as the denominator for percentage calculation. For OS, the number and percentage of patients who died or are censored will be summarized. In addition, duration of total follow-up will also be summarized.

Kaplan-Meier plots will be generated and the median, 25% and 75% percentile of PFS and OS will be estimated using the Kaplan-Meier method with their corresponding 95% confidence interval calculated based on the method by Brookmeyer and Crowley (1982). Additionally, Kaplan-Meier estimates will be provided for the survival probability along with their 95% confidence intervals (Kalbfleisch, 1980) at selected landmarks of 12, 18, and 24 months for PFS and OS.

Data listings will be generated for PFS and OS, respectively. Tumor scan data will be included in the PFS data listing, while the duration of total follow-up will be included in the OS data listing. For each listing, detailed information supporting the calculation of PFS (or OS) along with the censoring indicator, and reasons for censoring will also be included.

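### The SAP's duration of total follow-up is OS time without its censoring flag, so its median tracks median survival and does not show how long patients were observed for survival

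*SAP*

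**What the plan says.** SAP 7.4 gives the formula "Duration of total follow-up (months) = (date of death or date of last contact date known as alive", minus the date of Cycle 1 Day 1 (C1D1) plus 1, divided by 30.4375. SAP Table 3 gives the same definition. SAP 7.4 adds: "The summary statistics for this variable will be included in the summary table for the OS analysis".

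SAP 8.2.2, after the counts of deaths and censored patients, says: "In addition, duration of total follow-up will also be summarized". It names no method. SAP 4.2 supplies the default: "In general, continuous variables will be summarized descriptively, i.e., the following summary statistics will be presented". The list that follows is n, mean and standard deviation, median, quartiles, minimum and maximum. Protocol 12.4.6.2 also says only that total follow-up will be summarised.

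SAP 8.1.3 gives this definition of OS: "time (months) from the date of C1D1 to the date of death for patients who died in the study due to any cause". Survivors are counted up to their latest contact alive.

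On timing, SAP 2.1 says: "The final planned analysis will be conducted when approximately 70% of patients have died", which it puts at 21 deaths. On size, SAP 1.1 says: "The final total number of patients enrolled in this study is 30".

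Neither document plans a reverse Kaplan-Meier estimate, a summary of time from C1D1 to the cutoff, or a summary restricted to survivors.

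**The concern.** A median follow-up printed in an OS table is normally read as the length of time over which patients could have been seen to die. Readers use it to judge how far along the curve the estimates are well supported. SAP 8.2.2 plans Kaplan-Meier estimates at 12, 18 and 24 months, so the question will arise for the later OS landmarks.

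The SAP's variable does not answer it. A patient who dies at month 5 contributes 5 months, even if enrolled two years before the cutoff. With about 70% of patients dead, the table would show nearly the same information twice: once as the Kaplan-Meier median OS, and once as a raw median labelled follow-up. A printed value near 12 months would suggest that the 18- and 24-month OS estimates lie well beyond the period of observation, when typical observation time could be near 21 months.

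**Working it through.** **Inputs from the documents**
- Follow-up: C1D1 to death or last contact known alive (SAP 7.4, Table 3). OS time: the same dates, plus a censoring flag (SAP 8.1.3).
- Patients: 30 (SAP 1.1). Trigger: about 70% deaths (SAP 2.1).
- Reference median OS: 12.1 months, in historical patients without brain metastases on sacituzumab govitecan (Protocol 4.1).
- Accrual: estimated start in Q4 2021 (Protocol synopsis), closed 14 February 2023 (SAP 1.1), so about 14 to 16 months.
- Survival contacts about every 3 months (SAP 1.1).

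**Assumptions, because the documents are silent:** OS shape (exponential in the base case), dropout (none in the base case), uniform accrual, and median OS values above 12.1 months.

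**Step 1. The trigger.** 0.70 × 30 = 21 deaths, as the SAP states. For the planned 45 patients, 0.70 × 45 = 31.5, matching the protocol's 32.

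**Step 2. Closed form.** Suppose every patient has the same potential follow-up C and survival is exponential with median M. With 70% dead, C/M = ln(0.3)/ln(0.5) = 1.74. More than half have died, so the raw median of min(death time, C) is M. The shortfall against C is 1 − 1/1.74 = 42%, whatever M is. For M = 12.1 months, C = 1.737 × 12.1 = 21.0 months.

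**Step 3. Simulation.** Trials of 30 patients were cut at the 21st death, with 3000 runs per scenario. Entries are averages over runs, in months.

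| Median OS | Accrual | SAP median | KM median OS | Reverse-KM median | Median time to cutoff | Shortfall vs reverse KM |
|---|---|---|---|---|---|---|
| 12.1 | about 0 | 12.4 | 11.8 | 20.3 | 20.3 | 38% |
| 12.1 | 10 | 12.3 | 11.8 | 20.8 | 20.5 | 40% |
| 12.1 | 14 | 12.2 | 11.9 | 21.3 | 20.9 | 43% |
| 12.1 | 16 | 12.0 | 11.8 | 21.4 | 20.9 | 44% |
| 17.3 (assumed) | 10 | 17.7 | 16.9 | 29.7 | 29.4 | 40% |
| 17.3 (assumed) | 14 | 17.6 | 16.9 | 29.9 | 29.5 | 41% |
| 19.8 (assumed) | 14 | 20.4 | 19.5 | 34.4 | 33.9 | 40% |

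The SAP median was 1.02 to 1.05 times the KM median OS in these exponential, no-dropout scenarios. In the row for median OS 12.1 and 14-month accrual, the shortfall in single trials ran from 30% to 55% (10th to 90th percentile).

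**Step 4. Sensitivity at median OS 12.1**
- Last contact up to 3 months before the cutoff: 42%.
- Weibull shape 0.8: 48%. Shape 1.3: 38%. Shape 1.5: 36%. Shape 2.0: 33%.
- Assumed loss of 0.5% per month plus the contact gap: 48%.
- Assumed loss of 1% per month: 55%. The SAP median is then 0.86 of the KM median OS, because early losses also pull it down.

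**Step 5. Dependence on survival.** With 10-month accrual, raising median OS from 12.1 to 17.3 months moves the SAP median from 12.3 to 17.7 (a factor of 1.44) and the reverse-KM median from 20.8 to 29.7 (a factor of 1.43). Both move together, because the cutoff waits for deaths.

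**The case against.** The strongest reply is that the SAP miscalculates nothing. Section 7.4 says openly that the variable is the interval over which a patient took part in the study, and it measures that correctly. No passage says that it will be used to judge maturity. This stands: the shortfall is relative to reverse Kaplan-Meier or time to cutoff, not to a promise in the SAP. What remains is that the label, placed in the OS table, invites the usual reading.

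Second, the table shows more than a median. With median OS 12.1 months and 14-month accrual, the upper quartile averages about 18.2 months and the maximum about 26.1, which bracket the reverse-KM median of about 21. SAP 8.2.2 also plans counts of deaths and censored patients, curves, landmark intervals and a patient listing with the censoring indicator. An attentive reader could recover the missing figure. This lowers the severity, but the reader still has to do the work.

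Third, the size is not fixed. It rests on an assumed survival shape and dropout rate, and SAP 1.1 lets the sponsor stop at a different death fraction. This also stands.

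Two stronger readings are tempting. One is that the SAP figure is confounded with outcome and reverse Kaplan-Meier is not. At a death-driven cutoff this fails, because both rise with survival by almost the same factor. The other is that PFS maturity is misreported in the same way and cured by the same change. It is not: SAP Table 6 generally censors PFS at the last adequate scan, and reverse Kaplan-Meier on death times says nothing about scan follow-up.

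**Conclusion.** The point holds, with minor severity. The planned median follow-up is the raw median of OS times at a cutoff where about 70% have died. It therefore tracks median OS and does not show how long patients were under observation for survival. Assuming exponential survival and no dropout, it lies on average about 40% below the reverse Kaplan-Meier median (38% to 44% over the accrual periods and OS medians tried). Over the other shapes and loss rates tried, the average gap was about 33% to 55%. One trial of 30 can differ considerably from the average, and another death fraction at cutoff would change the gap.

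The consequence is limited to one descriptive figure, which matters for reading OS maturity, chiefly at the 18- and 24-month landmarks. A reader might infer that the PFS or OS results are themselves affected. The documents do not support that: both are estimated by Kaplan-Meier with their own censoring, and no estimate, interval or decision rule uses this variable.

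**What to change.** In SAP 7.4 and 8.2.2, state that median survival follow-up will be estimated by reverse Kaplan-Meier on the OS data, with deaths censored and censoring treated as the event, and reported with a 95% CI. Keep the present variable, if wanted, under the label *time on study*.

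This covers OS follow-up only. If a maturity figure for PFS is also wanted, apply the same method to the PFS times and the Table 6 censoring dates.

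The cost is a sentence or two in the SAP and one rerun of the planned OS procedure with the censoring flag reversed. No new data are needed. Protocol 12.4.6.2 leaves the method open and SAP section 1 gives the SAP precedence on methods, so no protocol amendment is needed. If the SAP is already signed off, that same section provides for recording the addition, with its rationale, in the clinical study report.

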8. EFFICACY ANALYSIS

All efficacy analyses will be performed for the FAS population, unless specified otherwise.

The primary efficacy endpoint for this study is the treatment effects on PFS. PFS and other efficacy endpoints related to tumor response (ORR, CBR, and DOR) and myeloprotection efficacy will also be evaluated based on data collected during the treatment period (see Section 2.1).

The treatment effect on OS will be evaluated when the number of events specified in Section 2.1 are observed for OS. The clinical database will be locked for this analysis. At the time of the final planned analysis, all other efficacy analyses outlined for the study will also be conducted.

8.1. Definitions of Efficacy Endpoints

8.1.1. Primary Efficacy Endpoints – Progression Free Survival

Progressive disease (PD) and tumor response status are programmatically determined according to RECIST v1.1 based on the radiographic tumor assessment data recorded on the eCRF by the Investigator for target lesions, the investigator assessment of non-target lesions, and the status of new lesions. For a patient, the status of PD will be determined using all radiographic tumor scan data assessed prior to or on the date of the data cutoff to conduct the analysis for PFS. In the situation where PD and withdrawal of consent or PD and initiation of subsequent anticancer therapy occurred on the same day for a patient, the PD status will be assumed for that patient.

Radiographic PD and death due to any cause during the study are referred to as PFS events.

PFS is defined as the time (months) from date of C1D1 to the date of the first documented disease progression, or death in the absence of PD for those who had a PFS event, and the time from date of C1D1 to the censoring date for those who did not have a PFS event. Specifically, PFS is calculated as (date of PFS event or censoring – date of C1D1+ 1)/ 30.4375. The analysis for PFS will be based on the FAS.

Details for PFS calculation and censoring rules can be found in Table 6.

Situation	Date of Event or Censoring	Outcome
Disease progression per RECIST Version 1.1	Date of the first documented progression	PFS event
Death without a PD	Date of death	PFS event
Incomplete or no baseline tumor assessments	Date of C1D1	Censored
No progression	Date of the last adequate radiological tumor assessment with no documented disease progression	Censored
Treatment discontinuation for reasons other than disease progression	Date of the last adequate radiological tumor assessment with no documented progression	Censored
Subsequent anticancer treatment started prior to documented disease progression	Date of last adequate radiologic assessment prior to or the date of initiation of subsequent anticancer treatment	Censored

Table 6PFS Calculation and Censoring Rules

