## 11.2. Efficacy Assessments

## 11.2.1. Anti-tumor Efficacy Assessment

All sites of measurable and non-measurable disease must be documented at Screening and re-assessed at each subsequent tumor evaluation. Tumor assessment will be performed at the timepoints relative to Cycle 1 Day 1, as specified in the Schedule of Assessments (Table 6), regardless of drug (cycle) delays, skips, or interruptions. Tumor assessments will continue until disease progression, withdrawal of consent, initiation of subsequent anti-cancer therapy, or study completion, whichever occurs first.

Baseline imaging must include CT or magnetic resonance imaging (MRI) of the chest, abdomen, and pelvis. CT scans with IV contrast are the preferred method unless contraindicated (i.e., patients with contrast allergy or impaired renal clearance) and oral contrast may be used per Investigator's discretion. MRIs of the chest, abdomen, and pelvis with a noncontrast CT scan of the chest may be used in patients for whom CT scans with contrast are contraindicated. Bone scan or positron emission tomography (PET) scan (such as [18F]-fluorodeoxyglucose [FDG]-PET, sodium fluoride [NaF]-PET, or other locally available PET options) must also be performed in all patients to evaluate for bone metastases at baseline. At the Investigator's discretion, other methods of assessment of measurable disease per RECIST v1.1 may be used. Any CT, MRI, or bone imaging (bone scan or PET scan) obtained as standard of care prior to Screening visit will not need to be repeated as long as those imaging tests were obtained within 30 days prior to the date of enrollment.

After baseline tumor assessments, evaluation of tumor response per RECIST v1.1 will be performed every 6 weeks for the first 36 weeks following Cycle 1 Day 1 ( $\pm$ 7 days) and every 9 weeks thereafter ( $\pm$ 7 days), with additional scans performed as clinically indicated.

Post-baseline tumor assessments should use the same imaging modality (CT or MRI) as at baseline. Patients with bone metastases identified on the baseline bone scan or PET scan should be followed at scheduled visits using localized CT or MRI as clinically indicated. If the patient has bone metastases on the baseline bone scan or PET scan but are not visualized on CT or MRI, the same bone imaging modality (bone scan or PET scan) should be repeated when a complete response is identified in target disease or when progression in bone is suspected (Table 6).

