#### 12.4.6. Efficacy Analyses

#### 12.4.6.1. Analyses of Primary Efficacy Endpoint – Progression-Free Survival

The primary efficacy endpoint of PFS during the study is defined as the time (months) from the date of first dose of study drug to the date of documented radiographic disease progression per RECIST v1.1 or death due to any cause, whichever comes first. PFS will be determined using all data until the last evaluable visit prior to or on the date of (i) radiographic disease progression per RECIST v1.1; (ii) withdrawal of consent to obtain additional scans on study; or (iii) initiation of subsequent anticancer therapy, whichever is earlier. Death (in absence of progressive disease [PD]) is always categorized as an event in the PFS analysis. Censoring rules for patients who do not experience PD or death at the data cutoff date will be described in the study SAP.

The primary analysis for PFS will be conducted at the time when 36 patients have radiographically-determined disease progression or have died. A Kaplan-Meier plot will be produced. The median, 25%, and 75% percentile of PFS will be estimated using the Kaplan-Meier method with their corresponding 95% CI calculated using the method by Brookmeyer and Crowley (1982).

Analysis of PFS during the study will be based on the FAS.

G1T28-213

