1. INTRODUCTION

This Statistical Analysis Plan (SAP) provides detailed statistical methods, variable definitions and derivations, and data handling that will be applied to analyze the clinical trial data collected during study G1T28-213, "A Phase 2, Single-Arm, Open-Label Study of Trilaciclib Administered Prior to Sacituzumab Govitecan-hziy in Patients with Unresectable Locally Advanced or Metastatic Triple-Negative Breast Cancer Who Received at Least Two Prior Treatments, at Least One in the Metastatic Setting" based on the protocol Version 2.0 (dated 15 November, 2021).

Statistical Programming Supportive Documents (SPSD) will be developed based on the SAP to serve as companion documents of the SAP to guide programming realization of the SAP. SPSD contain three separate documents:

- 1. The table of contents (TOC) for planned analyses (in Excel Spreadsheet).
- 2. The reporting conventions (in Word).
- 3. The shells or specificities for tables, listings, and figures (TLFs) generation (in Word).

Statistical software SAS[®] (SAS Institute Inc., Cary, NC) Version 9.4 or later will be used to perform data analyses following the plan as laid out in this SAP.

If there are differences between statistical analysis approaches described in the SAP and those in the protocol, the methods and approaches in the SAP will supersede those in the protocol. Changes and additions to the last signed off version of the SAP will be documented with corresponding rationale in the clinical study report (CSR).

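### SAP Table 6 can be read to censor at C1D1 a patient with an incomplete or absent baseline who later dies or progresses, and it discards event-free follow-up even on the milder reading

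*SAP*

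**What the plan says.** SAP Table 6 has six rows. Two are events: RECIST progression, dated at first documentation, and "Death without a PD", dated at death. Neither depends on baseline status. The third row, "Incomplete or no baseline tumor assessments", is censored at C1D1, also without condition. The last three rows (no progression, stopping treatment for another reason, subsequent anticancer treatment before documented progression) censor at the last adequate scan. No order of precedence is given, and incomplete is not defined.

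The text above the table says "Radiographic PD and death due to any cause during the study are referred to as PFS events". It measures PFS to the event for patients who had one, "and the time from date of C1D1 to the censoring date for those who did not have a PFS event".

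Protocol 12.4.6.1 says "Death (in absence of progressive disease [PD]) is always categorized as an event in the PFS analysis". What it leaves to the SAP is narrow: "Censoring rules for patients who do not experience PD or death at the data cutoff date will be described in the study SAP". SAP Section 1 adds that, where the two documents differ, "the methods and approaches in the SAP will supersede those in the protocol". SAP Section 10 lists no change to the PFS event rule.

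SAP Section 8.1.2 applies the Table 6 censoring rules to DOR as well.

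Protocol 11.2.1 requires baseline CT or MRI of chest, abdomen and pelvis, plus a bone scan or PET that "must also be performed in all patients to evaluate for bone metastases at baseline". The Schedule of Assessments row names CT/MRI only. Its footnote mentions baseline bone imaging without calling it mandatory.

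**The concern.** A baseline can be partly missing in a patient whose target lesions were measured and who can be followed by RECIST. A missing bone scan is the obvious case, because a site working from the schedule alone might omit it. Such a patient has received study drug, belongs to the full analysis set and can progress, respond or die. A programmer who applies the baseline row as written would remove that patient from the primary endpoint at day 1. At stake are lost PFS events, lost follow-up and, for DOR, a date that makes no sense. The study closed enrolment at 30 patients, so each one counts.

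**Working it through.** **1. Which rows apply.** For a treated patient with an incomplete baseline:

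| Later course | Rows that fit | Outcomes |
|---|---|---|
| Dies without progression | baseline; death | censored at day 1, or event at death |
| Documented progression | baseline; progression | censored at day 1, or event at progression |
| Neither | baseline; no progression | censored at day 1, or at last adequate scan |

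The first line conflicts with protocol 12.4.6.1 if the baseline row wins. The protocol's explicit sentence covers death only. For progression, the conflict is with the general PFS definition in both documents.

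**2. Does the SAP text settle it?** It gives a censoring date only to patients without an event, which favours the event rows. But the table does not always work that way: its last row censors a patient who started new treatment before documented progression, so a later progression is set aside. A programmer cannot conclude from the table that an event row always wins.

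**3. If events do win.** The third line of the table remains open. SAP 8.1.1 computes PFS as (date − C1D1 + 1)/30.4375. Take an event-free patient whose last adequate scan is at week 36, study day 36 × 7 + 1 = 253. The no-progression row gives 253/30.4375 = 8.31 months. The baseline row gives 1/30.4375 = 0.03 months.

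**4. DOR.** SAP 8.1.2 computes (end date − first response date + 1)/30.4375. Take a confirmed response first seen at the 6-week scan, study day 43. Censoring at C1D1 (day 1) gives (1 − 43 + 1)/30.4375 = −1.35 months.

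**5. Size.** Inputs from SAP 1.3: exponential PFS, control median 5.6 months, 10-month accrual, 14 months of follow-up after the last patient is dosed. With accrual taken as uniform and λ = ln 2/median, the probability of an observed event is

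p = 1 − [exp(−14λ) − exp(−24λ)]/(10λ).

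- Median 8.0: p = 0.801; 45p = 36.05 (SAP Table 2: 36).
- Median 7.0: p = 0.841; 45p = 37.86 (SAP Table 2: 38).

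The plan's event counts reproduce. For N = 30:

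- Median 8.0: 30 × 0.8011 = 24.0 events.
- Median 5.6: p = 0.899; 30 × 0.8986 = 27.0 events.

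Each patient censored at day 1 is 1/30 = 3.3% of the sample and costs 0.80 to 0.90 expected events. The number affected, k, is not in the documents. For assumed values at median 8.0: k = 1 leaves 24.03 − 0.80 = 23.2 events, k = 3 leaves 21.6, and k = 5 leaves 20.0.

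**6. Direction.** Censoring at day 1 removes the patient from the risk set as well as any event. Take five events at 2, 4, 6, 8 and 20 months: the Kaplan-Meier median is 6. Censor the 20-month patient at day 1 and survival reaches exactly 0.5 at 4 months, so the median falls to 5 by the midpoint convention. Censor the 2-month patient instead and it reaches 0.5 at 6 months, so the median rises to 7.

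**The case against.** The best reply is that the SAP already decides the matter. Its text defines any death or radiographic progression as an event and reserves censoring for everyone else, so a patient who dies never reaches a censoring row. The rows for no progression and for stopping treatment carry no exception for death either, and nobody would read them as censoring deaths. The clause giving the SAP priority operates only where the documents differ, and Section 10 announces no difference. Measurable disease and baseline imaging are required, and eligibility waivers are not permitted. Nothing shows that any patient falls in this row.

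Much of this stands. A reader might infer that the SAP deliberately censors deaths against the protocol; the documents do not say so, and read together they lean the other way. A reader might also infer that the row can only lengthen PFS; step 6 shows otherwise. Nor does any passage state that a missing bone scan makes a baseline incomplete.

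Three things survive. The subsequent-treatment row shows that the table does not always let an event win. The conflict for event-free patients does not depend on the event definition at all. And the DOR result is wrong whichever row wins for PFS events, as long as a responder can be censored at C1D1.

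**Conclusion.** The point holds as a defect in the rules for the primary endpoint: overlapping rows with no hierarchy and an undefined term. One available reading contradicts protocol 12.4.6.1 and the SAP's own definition. The milder reading still discards usable follow-up, and DOR can come out negative.

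The practical effect is probably small, because few patients should lack a complete baseline. Per affected patient it is 3.3% of the sample and about 0.8 to 0.9 expected PFS events. The event figure assumes the original accrual and follow-up carry over to 30 patients; the analysis is now triggered by about 21 deaths, so actual follow-up may differ. The bias can go either way, depending on the prognosis and event status of the affected patients. Loss of power is not the issue, because the SAP plans Kaplan-Meier description of PFS and no test. The change should be made because it is cheap and restores the protocol's own rule.

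**What to change.** In SAP Table 6:

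- Restrict C1D1 censoring to patients with no baseline tumor assessment and no documented progression or death.
- State that death, and documented progression not preceded by subsequent anticancer therapy, take precedence over the baseline row.
- Assess patients with measured target lesions but an otherwise incomplete baseline under the remaining rows.

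In SAP Section 8.1.2, state that the C1D1 row does not apply to DOR.

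The cost is one edited table row and two or three sentences, with no new data collection. It should be done before database lock. Reporting how many patients had an incomplete or absent baseline would show whether the rule mattered.
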